### Study Assessments

Safety Assessment:

[figure not shown]
- History, physical exam, and routine blood work such as blood counts and comprehensive metabolic panel will be performed on day 1 of each treatment cycle. Echocardiograms and ophthalmologic examinations will be performed periodically for those on the cobi arm.
- Analyses will be performed for all patients having received at least one dose of study drugs. The study will use the NCI CTCAE v5.0.

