### 3.7.2.3 Dose-Limiting Toxicities

In Study NP27872, 31 dose-limiting toxicity (DLT) AEs were reported and 21 of 99 patients (21.2%) experienced at least one DLT AE. The SOCs affected by DLT AEs were blood and lymphatic system disorders (19 patients, 19.2%), gastrointestinal disorders (3 patients, 3%), and investigations (1 patient, 1%). The most frequently reported DLT AE was thrombocytopenia or

platelet count decreased (17 patients, 17.2%). Additionally, neutropenia (5 patients, 5.1%), febrile neutropenia (3 patients, 3.0%), and nausea (2 patients, 2%) were reported. Three of thirtysix patients (8.3%) on the weekly schedule experienced DLT AEs, whereas 6 of 15 patients (40%) and 11 of 34 patients (32%) on the daily schedules for 3 days and 5 days, respectively, experienced DLT AEs. DLTs from the blood and lymphatic system disorder were more frequently reported with the daily dosing schedules than with the weekly dosing schedule. DLTs were not assessed in Study NP28902 and Study NP29910.

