# 6. STUDY CALENDAR

		Week/Cycle											
Parameter	Pre- Treatment 	C1 D1	C1D8	C1 D15	C1 D1,8, 15, 22 	C2 D1	C2 D15	C3D1	D1 Every Cycle	D15 Every Cycle	Day 1 of Every Odd Cycle except Cycle 1	Every 12 weeks from C2D1 onwards	End of Treatment 
Demographics	х												
	,				CLIN	IICAL EV	ALUATION	IS:					,
History and Physical	x				x		X12		х				х
Height	х												
Vital signs and Weight 	х				х		X12		х	х			х
Performance status	х				х		X12		х				х
Ophthalmologic evaluation 	х					х						х	
				L	ABORATOR'	Y/RADIOI	LOGIC EV	LUATION	IS:	"			
Hematology (CBC/diff, plt)	х				Х		X12		х				
Comprehensive Metabolic Panel 	х			х	Х		X12		х				
Pregnancy Test 	х										х		
Phosphorus		х							х				
Uric Acid		х							х				
СРК	х								х				
Amylase/ Lipase	х										х		
Echocardiogram 	х					х						х	
Thyroid Stimulating Hormone (TSH)	х								х				
HCV antibody and HBV surface antigen	х												
TP53 status 	х												
Tumor Assessments through Imaging Studies 	х										х		

		Week/Cycle											
Parameter	Pre- Treatment 	C1 D1	C1D8	C1 D15	C1 D1,8, 15, 22 	C2 D1	C2 D15	C3D1	D1 Every Cycle	D15 Every Cycle	Day 1 of Every Odd Cycle except Cycle 1	Every 12 weeks from C2D1 onwards	End of Treatment 
			•		TREAT	MENT A	OMINISTRA	TION		•		•	
Atezolizumab			IV once every 2 weeks starting on Cycle 1 Day 15										
Cobimetinib ( TP53 -mut arm)			PO once daily from Day 1 – 21 starting on Cycle 1 Day 1										
ldasanutlin ( TP53- wt arm)		PO once daily from Day 1 – 5 starting on Cycle 1 Day 1											
					COF	RRELATI	/E STUDIE	S:					
Tumor Biopsy 	х			х									
Blood collection 		х		х				х					х
ADDITIONAL INFORMATION:						·							
Concomitant Medications Review		х							х	х			х
Adverse Events Assessment							X (AE will	be assess	sed through	hout the st	udy)		

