#### Note:

- ☐ Additional tests may be performed at the discretion of the treating investigator as clinically indicated.
- The sample collection schedules outlined above are based on an ideal subject. The sample schedule should be followed as closely as is realistically possible; however, the schedule may be modified (± 4 business days) due to problems such as scheduling delays or conflicts (e.g., clinic closure, poor weather conditions, vacations, etc.).
- □ Items highlighted in grey are performed for research purposes (not standard of care)
  - 1. Within 4 weeks prior to starting treatment, unless otherwise noted.
  - 2. Serum chemistry includes measurement of sodium, potassium, chloride, bicarbonate, BUN, creatinine, glucose, total bilirubin, calcium, total protein, albumin, AST, ALT, and alkaline phosphatase.
  - 3. On days of Atezolizumab treatment, Pre-Dose vitals should respectively be recorded ≤ 60 minutes prior to the start of the Atezolizumab infusion. Post-Dose vitals should be recorded during and after infusion only if clinically indicated.
  - 4. Baseline evaluation of disease status by CT or MRI within 28 days prior to first dose of study drugs. Baseline and subsequent scans to include imaging of the chest, abdomen and pelvis. The first scheduled re-scan should be performed and evaluated 7 to 8 weeks after Cycle 1, Day 1 treatment, with subsequent scheduled scans intended every ~ 8 thereafter. Scanning on the same day as dosing is discouraged but allowed, provided scan results receive appropriate evaluation prior to study

- treatment. Additional disease evaluations or increased scan frequency may be performed according to the medical judgment of the patient's study physician.
- 5. Fresh biopsy in consenting patients (including those with pre-existing archival tissue) with primary or metastatic lesion judged amenable to medically safe excisional, incisional or core needle biopsy.
- 6. A 1-month follow-up clinic visit is intended 28 days (±7 days) after the preceding End-of-Treatment visit. Documented attempt(s) should be made for patient return to the study clinic. It will not be considered a protocol deviation if the patient is physically unable to return for the follow-up visit; such circumstance should be recorded in the study documents, and as much of the follow-up information as possible should be obtained via feasible patient contact and from local and outside facilities.

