- 7. If a patient discontinues the study for reason other than progressive disease confirmed by CT or MRI (e.g. adverse event), then CT or MRI scans of the chest, abdomen and pelvis should be continued every 8-9 weeks until disease progression is confirmed by imaging.
- 8. For tissue collection, refer to Lab Manual for details of collection, processing and shipping.
- 9. For peripheral blood, refer to **Lab Manual** for details of collection, processing and shipping
- 10. Please note on Section 10 and Lab Manual that both FFPE and fresh tissue should be obtained.
- 11. Complete ophthalmologic exams will be performed prior to treatment initiation, cycle 2 day 1 (± 1 week), and every 12 weeks from then on (± 2 weeks) on patients in the cobimetinib arm only. Complete ophthalmologic examination will be performed and interpreted by a qualified ophthalmologist, including visual acuity testing, intraocular pressure measurements by tonometry, slit-lamp ophthalmoscopy, indirect ophthalmoscopy, and spectral domain optical coherence tomography. Ophthalmologic examination may be performed up to 42 days prior to starting study treatment.
- 12. For patients on the phase Ib portion of the study only (idasanutlin arm only)
- 13. Only for women of childbearing potential
- 14. Evaluation of LVEF by Echocardiogram should be performed prior to treatment initiation, cycle 2 day 1 (± 1 week), and every 12 weeks from then on (± 2 weeks) on patients in the cobimetinib arm only. The treatment discontinuation visit evaluation of LVEF does not need to be performed at the treatment discontinuation visit if an evaluation has been performed within the last 12 weeks and there are no clinically significant findings and/or changes from baseline. All patients restarting treatment with a dose reduction of cobimetinib because of a decrease in LVEF should have LVEF measurements taken after approximately 2 weeks, 4 weeks, 10 weeks, and 16 weeks, and then resume monitoring of LVEF every three treatment cycles. Any patient who develops clinical signs or symptoms suspicious of cardiac failure should undergo an LVEF assessment.
- 15. *TP53* mutation status may be known based on previously checked NGS or cfDNA commercially available assays. If not known, an archival FFPB should be sent to the Sponsor (see Section 10 and **Lab Manual**) for *TP53* mutation status determination.

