#### 8.3.2.2. Hematological Toxicities

Patients treated with idasanutlin are at increased risk for infections for the effect on bone marrow progenitors and the related cytopenia. Patients should be closely monitored for infection, and prompt therapy and diagnostic procedures need to be performed as necessary. Idasanutlin has exposure-dependent suppressive effects on bone marrow progenitors. Prophylactic platelet transfusion is recommended when platelet count is < 10 x109/L or local institutional guidelines, and therapeutic transfusions are recommended when clinically indicated (any platelet value in the presence of hemorrhagic symptoms). The hemoglobin level should be maintained at > 9 g/dL in patients with documented cardiac insufficiency (ejection fraction < 50%). Growth factor support may be given per local guidelines for hematologic or solid tumor malignancies.

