# \*\*Specimens should be mailed to arrive from Monday 8AM through Friday 1PM\*\*

## 10.3. Tissues Samples

At screening: patients will provide a signed informed consent form prior to any study related activities. Patients with known *TP53* mutation status (by previously performed NGS or cfDNA) will not be required to wait to initiate study treatment provided all other screening procedures have been completed. For patients without known *TP53* mutation status, an archival tissue (FFPE from primary or metastatic lesion) should be sent to the Sponsor (see sections 10.3.1 – 10.3.3 for details on tissue submission requirements and testing procedures), and once tissue is received, results for *TP53* status will take an average of 2 weeks and will be communicated to the site.

On study: Fresh tumor biopsies will be collected in patients (a) prior to initiating Cobimetinib or Idasanutlin (PRE-Bx), and (b) after 15 days of Cobimetinib or Idasanutlin but prior to adding on Atezolizumab (POST-Bx). One tumor core will be fixed for IHC analysis, while two additional cores will be snap-frozen for RNA and DNA extraction where feasible. The fresh biopsies will follow guidelines as listed in the **Lab Manual**. The molecular correlates for each biological sample/time point are listed below.

Correlate	Sample Source	Test	Needs immediate specialized processing	Needs immediate shipping
TILs				
CD8				
CD4				
HLA-A (MHC-I)	FFPE tumor			
IHC	biopsy	IHC/multiplexed IF		
HLA-DR (MHC-II)	Diopsy		NO	NO
IHC				
FoxP3				
PD-L1				
RNA-seq	Fresh frozen	RNA		
Exome-seq	tumor biopsy	DNA		

Parameter	Prior to Cycle 1 Day 1	Cycle 1 Day 15
Immunohistochemistry (IHC) Analysis	X	X
RNA-seq	X	X
Exome-seq (tumor)	X	
TCR Sequencing	X	X

Tissue specimen labeling, documentation and shipment

- Label ALL specimens before freezing
- If sample comes in contact with contaminate, make note in information section of paperwork.
- Enter time core biopsy was collected on paperwork.
- Label each collection containers with Patient ID sequence number/code letter, Medical Record #, site and location of biopsy, date and time.
- Ship specimens along with Tissue/Blood Registration Form directly to:

[name]. Ph.D [name] [name] Office [contact]

Research Lab [contact]

The specimens will be logged in as a consented specimen and either be stored frozen or as paraffin-embedded tissue and available for molecular pathology studies.

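### Patients enrolled directly into Phase II reach the Cycle 1 Day 15 biopsy and first atezolizumab infusion with no scheduled platelet count since Day 1

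*Combined protocol and SAP*

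**What the plan says.** The calendar row "Hematology (CBC/diff, plt") is marked in four places: pre-treatment, the weekly Cycle 1 column (Days 1, 8, 15 and 22), Cycle 2 Day 15, and Day 1 of every cycle. The weekly column and the Cycle 2 Day 15 mark both carry footnote 12, "For patients on the phase Ib portion of the study only (idasanutlin arm only"). The row's cells in the separate Cycle 1 Day 15 column, which applies to all patients, and in the column for Day 15 of every cycle are blank. The synopsis (Study Assessments) agrees: "routine blood work such as blood counts and comprehensive metabolic panel will be performed on day 1 of each treatment cycle".

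The Cycle 1 Day 15 column for all patients does schedule a metabolic panel, a correlative blood draw and a tumor biopsy. Footnote 2 gives the panel's contents: "Serum chemistry includes measurement of sodium, potassium, chloride, bicarbonate, BUN, creatinine, glucose, total bilirubin, calcium, total protein, albumin, AST, ALT, and alkaline phosphatase". Section 10.3 places the second biopsy "after 15 days of Cobimetinib or Idasanutlin but prior to adding on Atezolizumab (POST-Bx"), and the first atezolizumab infusion is also set for Cycle 1 Day 15. The calendar notes add that "Additional tests may be performed at the discretion of the treating investigator as clinically indicated".

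On the hazard, Section 8.3.2.2 states that "Idasanutlin has exposure-dependent suppressive effects on bone marrow progenitors". For Study NP27872, Section 3.7.2.3 names platelet falls as the most frequent dose-limiting toxicity and reports that "DLTs from the blood and lymphatic system disorder were more frequently reported with the daily dosing schedules than with the weekly dosing schedule".

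**The concern.** The first biopsy falls in a screening period that includes a count and an eligibility floor of 100 × 10⁹/L platelets (Section 4.1). The second comes after a drug the protocol describes as marrow-suppressive, with no count required. The protocol does guard against biopsy bleeding elsewhere: exclusion criterion 13 allows therapeutic heparin only if it can be safely interrupted for biopsies. The main stake is the safety of the individual patient at Day 15.

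A second stake is the dose rules. Section 8.5 bases changes on the worst preceding toxicity. Grade 3 thrombocytopenia that resolves within 7 days requires a one-level reduction. Grade 4, or Grade 3 that lasts longer or comes with bleeding, requires discontinuation. A transient Grade 3 or 4 fall that has recovered by Cycle 2 Day 1 could go unseen. The rule would then not be triggered, and the next idasanutlin course could start at full dose. The event would also be absent from the adverse event profile, which is a secondary endpoint.

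**Working it through.** The plan gives no figure for this point, so the check is a reading of the calendar followed by simple counting.

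**Scheduled counts in cycle 1.** Cycles last 28 days, so Cycle 2 Day 1 is Day 29. Days are nominal, before the ±4 business-day window.

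| | Phase Ib idasanutlin | Direct Phase II | Direct Phase II with a Day 15 count |
|---|---|---|---|
| Days with a count | 1, 8, 15, 22, 29 | 1, 29 | 1, 15, 29 |
| Counts after Day 1 and before Day 29 | 3 | 0 | 1 |
| Longest interval | 8 − 1 = 7 days | 29 − 1 = 28 days | 29 − 15 = 14 days |

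**Age of the last scheduled count at the biopsy.** 15 − 1 = 14 days. Idasanutlin is given on Days 1 to 5, so the last dose was 15 − 5 = 10 days earlier.

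**Other Day 15 blood work.** The metabolic panel is chemistry only, as footnote 2 shows. The other draw is correlative: cell-free DNA and flow cytometry (Section 10.2.1). Neither is a blood count.

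**Patients with the gap.** Section 24.3.1 sets 16 patients for stage I and at most 33 per arm. Section 24.1 requires at least 6 patients at the recommended dose and counts them in Phase II.

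- Idasanutlin, 6 carried over: 16 − 6 = 10 to 33 − 6 = 27.
- Idasanutlin, 3 carried over: 16 − 3 = 13 to 33 − 3 = 30. This applies if dose level 3 is accepted after 0 of 3 dose-limiting toxicities, which Section 7.6 and the escalation table in 24.1 also permit.
- Cobimetinib: 16 to 33.

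The lower ends are floors, because accrual is not halted at the interim analysis. All of these figures count patients with the calendar gap. The number actually biopsied may be smaller, since footnote 5 limits biopsy to consenting patients with a lesion judged safe to sample.

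**Evidence of the hazard.** In NP27872, platelet dose-limiting toxicities occurred in 17/99 = 17.2% and thrombocytopenia of Grade 3 or higher in 29/99 = 29.3%. In NP28902, platelet falls of Grade 3 or higher occurred in 5/61 = 8.2% (Sections 3.7.2.3 and 3.7.2.4). These rates pool other doses and schedules and cover any time on treatment. They show that the effect exists; they do not give a Day 15 risk in this trial.

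**The case against.** The strongest reply is that the step-down in monitoring is deliberate and that several safeguards surround it.

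- The Phase II dose is chosen in Phase Ib with weekly counts and explicit platelet criteria (Section 7.5).
- Section 3.7.2.7 puts the doses at 50 to 200 mg, at most 200/250 = 80% of the 250 mg maximum tolerated dose for the 5-day schedule, and the marrow effect depends on exposure. (Section 9.3.3 gives 300 to 500 mg, a separate inconsistency.)
- Section 8.5 asks for laboratory values to be reviewed around each infusion, and extra tests are permitted.
- Biopsy conduct is referred to the Lab Manual, which may require a count.
- The documents give no time of platelet nadir, so Day 15 is not shown to be the point of greatest risk.
- The Cycle 2 Day 1 count would catch any cytopenia that persists.
- Later Phase II cycles also have Day 1 counts only, so a single added count does not secure the dose rules.

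Much of this stands as context. It lowers the likely frequency of harm and rules out any event probability. It also makes the dose-rule argument secondary: a fall that starts and recovers within either 14-day half of the cycle would still be missed, and the added count covers only cycle 1. But none of it supplies a required count. Reviewing laboratory values does not produce a platelet result if none was ordered. The weekly repeats in Section 7.5 start only once a cytopenia has been found. Phase Ib data inform the choice of dose, not one patient's platelets before a biopsy. If the Lab Manual does require a count, putting it in the calendar costs almost nothing.

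**Conclusion.** The concern holds. On the calendar and synopsis as written, a patient enrolled directly into Phase II has no scheduled blood count between Cycle 1 Day 1 and Cycle 2 Day 1. That is a 28-day interval containing the second biopsy and the first atezolizumab infusion. It affects 10 to 27 idasanutlin patients if 6 carry over from Phase Ib, or 13 to 30 if 3 do.

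The same gap applies to 16 to 33 cobimetinib patients, but with weaker grounds. These are a general hemorrhage warning (Sections 7.7 and 8.2.1.7) and hematology dose rules shared with idasanutlin (Section 8.5). Thrombocytopenia is not among that drug's listed common toxicities.

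The conclusion is limited to what the documents schedule; a requirement in the Lab Manual or in local practice cannot be excluded. This is a patient-safety improvement worth making. It does not affect the primary analysis.

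**What to change.** Mark hematology (blood count with differential and platelets) in the Cycle 1 Day 15 column for all patients, as is already done for the metabolic panel. State that the result is reviewed before the biopsy and before the first atezolizumab infusion, and align the synopsis sentence. The cost is one calendar cell, one extra tube at a visit where blood is already drawn, and an occasional short delay while the result is awaited. The change puts a platelet result in hand before the biopsy, and it narrows the window for an unseen nadir without closing it.

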## 7. TREATMENT PLAN

## 7.1. Overview

This is a multicenter, open-label, 2-arm phase Ib/II trial that will evaluate the anti-tumor effect of Atezolizumab (an anti- PD-L1 mAb) in combination with Cobimetinib (a MEK inhibitor) in patients with TP53-mutated ER+ mBC, or Idasanutlin (an MDM2 antagonist) in patients with TP53-wt ER+ mBC. In the phase Ib portion of the trial we will determine the safety and tolerability [Dose Limiting Toxicity (DLT), Maximum Tolerated Dose (MTD) and Recommended Phase II Dose (RP2D)] of Atezolizumab and Idasanutlin in patients with ER+ mBC. With three possible dosing cohorts, a minimum of 9 and a maximum of 18 subjects may be recruited for the dose escalation portion of the study. In the phase II portion of the trial we will determine the anti-tumor effect and adverse event profile of Atezolizumab with Cobimetinib or Idasanutlin in patients with ER+ mBC [Progression Free-Survival (PFS), Overall Response Rate (ORR; by RECIST 1.1) and/or Clinical Benefit Rate (CBR; percentage of patients without disease progression at 6 months); immunerelated Response Criteria (irRC), Percentage of patients alive at 12 months (% OS), and Adverse Event profile]. All participants will have targeted Next Generation Sequencing (NGS) performed prior to treatment arm allocation for TP53 mutation status determination and assess tumor mutation burden. We would expect about ~ 40% of all patients with ER+ mBC to have a TP53 mutation (TP53-mut) in their tumor3. For the phase II portion of the trial, a minimum of 33 and a maximum of 66 patients (total in both arms) will be receive study drugs (atezolizumab with cobimetinib or idasanutlin, based on TP53 mutation status) until disease progression. unacceptable adverse event(s), concurrent illness that prevents further administration of treatment, patient withdrawal from study, or significant non-compliance with protocol. To assess the anti-tumor effect of therapy, we will estimate the overall tumor burden at baseline to which subsequent measurements (performed every 8 weeks using the Solid Tumor Response Criteria [RECIST] v1.1) will be compared. Tumor biopsies (fixed for IHC analysis and snap-frozen for RNA extraction) and peripheral blood will be collected prior to initiating Cobimetinib/Idasanutlin (PRE-Bx), and after 15 days of Cobimetinib/Idasanutlin, prior to adding Atezolizumab (POST-Bx).

## 7.2. Screening Phase

At screening, the patient will provide a signed informed consent form prior to any study related activities. Patients with known TP53 mutation status (by NGS or cfDNA) will not be required to wait to initiate study treatment provided all other screening requirements have been met. For patients without known TP53 mutation status, archival tissue (FFPB from primary or metastatic lestion) should be sent to the Coordinating Center (see Section 10 for details on tissue submission requirements and testing procedures), and once tissue is received at the Coordinating Center, results for TP53 status will take an average of 2 weeks. Once patients are deemed eligible and TP53 mutation status is known, participants should begin study treatment consistent with the protocol, as soon as possible, but no later than 2 weeks after authorization to start treatment is given by the VICC Coordinating Center.

## 7.3. Allocation Procedures

Once eligibility is confirmed and TP53 mutation status is known, patients will then be allocated to receive:

 Arm 1 (TP53-mut) –Atezolizumab 840 mg IV, on Days 1 and 15, and Cobimetinib 60 mg PO daily, on Days 1 - 21, every 28 days; or

 Arm 2 (TP53-wt) –Atezolizumab 840 mg IV. on Davs 1 and 15, and Idasanutlin (final dose to be determined by the phase Ib portion of the trial) PO daily, on Days 1 - 5, every 28 days,

Note that on cycle 1 (in both arms) Atezolizumab will start on Cycle 1 Day 15 instead of Day 1.

## 7.4. Agent Administration

The investigator will instruct the patient to take the study drugs exactly as specified in the protocol. A pill diary will be given to all patients enrolled in the study. A cycle will last 28 days.

	1 cycle = 28 days				
N of pts.  Dose Level (IV q15 days)  Cobimetinib Idasanutlin (PO daily x 21 out of 28 days)  Cobimetinib Idasanutlin (PO daily x 5 out 28 days)		(PO daily x 5 out of			
			Phase Ib		
3-6	3	840 mg		200 mg	
3-6	2	840 mg		150 mg	
3-6	1	840 mg		100 mg	
3-6	–1	840 mg		50 mg	
	Phase II				
40		840 mg	60 mg		
40		840 mg		TBD	

